1.1 Background and Rationale

Added:

Currently Until 2023, fulvestrant was the only US Food and Drug Administration (FDA)-approved SERD. Fulvestrant is indicated for the treatment of patients with metastatic or advanced hormone-positive (HR+) breast cancer (Wang 2020) and has validated the important link between ER degradation and disease control.

In 2023, an oral SERD, elacestrant, was approved by the FDA for the treatment of ERpositive, HER-2 negative, ESR1 mutated advanced or metastatic breast cancer (FDA 2023).5.1 Treatment Plan and 8.1.2 Preparation and Administration of AC699

Section 5.1 Treatment Plan

Study Drug: AC699

CONFIDENTIAL

Sponsor/Development Innovations Study Numbers: AC699-001/BRE 401

All patients entering this study will receive AC699 orally (PO). The time of day for administration of AC699 should be consistent. The drug should be taken whole with liquid(s) and with food in the morning. The patient should avoid taking other medications at the same time as AC699. When possible, the patient should take other medications in the evening or separated by a minimum of 4 hours following AC699 dosing. If having the patient delay taking other medications 4 hours following AC699 dosing is not feasible please discuss with the Medical Monitor and document.

5.4.2 Prohibited Concomitant Medications

• Any new or concomitant QT prolonging medications within the last 6 months.

7.2 Screening

- ECHO (This **test** may be also be performed subsequently in the study repeated as clinically indicated.) A MUGA scan maybe obtained in place of an ECHO to determine ejection fraction.
- Estradiol and FSH levels to document post-menopausal status (female patients only <60 years of age who do not meet other criteria for post-menopausal status)

Referenced in the SOA Flow Chart Footnotes

7.2 Screening, 7.3.1 Cycle 1, 7.3.2 Day 1 of Subsequent Cycles, and SOA Flow Chart

• Biochemistry (sodium, potassium, phosphate, chloride, creatinine, total calcium, **total CO₂ or** venous bicarbonate [HCO₃], albumin, total protein, AST, ALT, ALP, bilirubin, lactate dehydrogenase [LDH], glucose, creatinine kinase [CK: if CK is elevated, **and elevation is clinically significant in the judgment of the Investigator**, then CK-MB, troponin I, and myoglobin should be reactively tested, with further follow-up as clinically warranted], urea nitrogen, and uric acid)

Referenced in the SOA Flow Chart Footnotes

7.3.3. Biomarkers (circulating tumor [ctDNA] and circulating tumor cells [CTC]) - Assessments Every 2 Cycles

Patients will be evaluated with CTC and ctDNA assessments pre-dose, on Day 1 of Cycle 1 and Cycle 2, and on Day 1 of all even numbered cycles thereafter. The biomarker assessments should also be collected at the EOT visit. for response to treatment after 2 cycles of treatment. Response will be 16 weeks (±5 days) thereafter. until progressive disease (PD) or another withdrawal criterion is met. Patients with PD or unacceptable toxicity should be discontinued from the study; patients with stable disease (SD) or response to therapy will continue treatment. The assessments to be performed at this time are specified in Appendix B. Please refer to Section 9 for further instructions on evaluating response (e.g., PD, SD).

Referenced in the SOA Flow Chart Footnotes

7.3.4 Imaging Assessments

Patients will be evaluated for response after 2 cycles of treatment. Response will be assessed every 2 cycles / 8 weeks (± 5 days) for the first year of treatment, and then every 4 cycles / 16 weeks (± 5 days), thereafter.

The following assessments will be performed if abnormal at baseline or if clinically indicated: CONFIDENTIAL

Study Drug: AC699 Sponsor/Development Innovations Study Numbers: AC699-001/BRE 401

• CT scan of chest/abdomen/pelvis to include adrenal glands (CT scan of abdomen and pelvis required if adrenal glands are not included on CT scan of chest). An MRI may be performed in place of a CT scan at the discretion of the Investigator. However, the same imaging modality should be used throughout the study to image a given lesion.

Referenced in the SOA Flow Chart Footnotes

7.7 Pharmacokinetic Assessments

Should a patient require a dose change, additional PK samples to ensure safety and efficacy parameters, may be required. These PK samples will be collected at the first cycle following the dosing change, at the same time points as Cycle 1 Day 1 and Cycle 1 Day 15. Subsequent pre-dose PK samples may be requested at the next 3 cycles following the dosing change. Decisions as to whether or not these samples are to be collected will be determined in consultation with the Medical Monitor.

Referenced in the SOA Flow Chart Footnotes

8.1.2 Preparation and Administration of AC699

All patients entering this study will receive AC699 PO. The drug should be taken whole with liquid(s) and with food. The patient should avoid taking other medications at the same time as AC699. When possible, the patient should take other medications in the evening or separated by a minimum of 4 hours from AC699 dosing. If having the patient delay taking other medications 4 hours from AC699 dosing is not feasible please discuss with the Medical Monitor and document.

The time of day for administration of AC699 should be consistent. On PK collection visits, patients should be instructed to bring the study medication with them to the clinic and will take the dose after the pre-dose PK is been-taken. If the patient misses a dose of study drug, the patient should take the dose as soon as possible, but not less than 12 hours before the next dose is due. If the next dose is due in less than 12 hours, the patient should skip the missed dose and take the next dose as scheduled.

Appendix F: PK Sampling Timepoints

Footnotes added:

Additional unscheduled PK samples may be drawn during the study for safety reasons. Should a patient require a dose change, additional PK samples to ensure safety and efficacy parameters, may be required. These PK samples will be collected at the first cycle following the dosing change, at the same time points as Cycle 1 Day 1 and Cycle 1 Day 15. Subsequent pre-dose PK samples may be requested at the next 3 cycles following the dosing change. Decisions as to whether or not these samples are to be collected will be determined in consultation with the Medical Monitor.

Appendix B: Response Evaluation Criteria in Solid Tumors (RECIST) Version 1.1

Special notes on response evaluation

Confirmation of response: Confirmation of response (by repeat scans after a **minimum of 4** weeks or as specified in the protocol—note, for the purpose of this protocol, it is after 4 weeks) is required for studies in which response rate is the primary endpoint, but is not required in

CONFIDENTIAL

Sponsor/Development Innovations Study Numbers: AC699-001/BRE 401

Final Protocol: 07 May 2024 Version 4.0

randomized studies or studies with primary survival endpoints (i.e., where response is not a primary endpoint).

Appendix C: Guidelines for Women of Childbearing Potential and Fertile Male Patients Women

Postmenopausal is defined as:

• 6 months of spontaneous amenorrhea with serum FSH levels > 40 mIU/ml and an estradiol value in the post-menopausal range per institutional standards <40 pg/mL (140 pmol/L), or

Appendix G: Clinical Protocol Amendment AC699-001/BRE 401 Summary of Change

The Summary of Change section has been moved from the front of the protocol to Appendix G.

Final Protocol: 07 May 2024 Version 4.0

Additions to the text are **bolded**, and deletions from the text are crossed off. Only the parts of sections with changes are presented. Please note that formatting changes and minor changes to punctuation, spelling, and abbreviations that do not affect meaning are not noted in this summary.

Synopsis and Section 3.1 Inclusion Criteria

- 1. Written informed consent, according to local guidelines, signed and dated by the patient or by a legal guardian prior to the performance of any study-specific procedures, sampling, or analyses
- 3. Female patients only: must be post-menopausal; as defined by:

2.0

- 9. Age \geq 60, or
- 10. Spontaneous amenorrhea (i.e. in the absence of chemotherapy, tamoxifen, toremifene, or ovarian suppression) for ≥12 months following cessation of all exogenous hormonal treatment, or
- 11. 6 months of spontaneous amenorrhea with serum follicle-stimulating (FSH) levels >40 mIU/ml and an estradiol value <40 pg/mL (140 pmol/L), or
- 12. Prior bilateral oophorectomy performed at least 6 weeks before screening, with or without hysterectomy, or
- 13. On a stable dose of a luteinizing hormone releasing hormone (LHRH) agonist ≥4 weeks
- 11. Acceptable organ function, as evidenced by the following laboratory data:
 - Renal function, as follows:
 - o Creatinine ≤1.5 × upper limit of normal (ULN), or Creatinine clearance of ≥60 mL/min by the Cockcroft-Gault equation or equivalent

Synopsis and Section 3.2 Exclusion Criteria

- 1. Treatment with any of the following:...
 - Proton pump inhibitors should not be used within at least 48 hours prior to C1D1 and are prohibited during the study.
- 5. Any of the following cardiac criteria currently or within the last 6 months:
 - Mean resting corrected QT interval (QTc) >480 470 msec...

Section 5.1.2 Intra-patient dose adjustment

Patients may be permitted an intra-patient dose-escalation of AC699 to a higher dose level that **does not have any treatment-related AE of Grade 3 or higher and** has been cleared and deemed safe by the SRC if they have completed Cycle 1 at their assigned dose level and continued on-study with no \geq Grade 2 treatment-related AEs.

CONFIDENTIAL

Sponsor/Development Innovations Study Numbers: AC699-001/BRE 401

Final Protocol: 07 May 2024 Version 4.0

Section 5.2 End of Study Treatment (EoT)

Patients will be discontinued from study treatment for any of the following reasons:...

Pregnancy

Section 5.4.1 Permitted Concomitant Medications and Therapy

• Luteinizing hormone releasing hormone agonists will be allowed.

Medicinal products that alter the pH of the upper GI tract may alter the solubility of AC699, expected to impact and limit its bioavailability. Such agents include, but are not limited to, proton pump inhibitors (e.g., omeprazole), H2-antagonists (e.g., ranitidine) and antacids. Proton pump inhibitors are prohibited (see Section 5.4.2). For patients who require mandatory use of antacid medication, proton pump inhibitors must be replaced with H2-antagonists or antacids. If H2 antagonist or antacid is used, study drug should be taken ≥ 2 hours before or 10 hours after dosing with H2-antagonists. Antacids, locally-acting acid neutralizing agents intake, are to be separated from study drug doses by 2 hours.

Section 5.4.2 Prohibited Concomitant Medications

• Proton pump inhibitors are prohibited due to their long PD effect. This type of drugs should be replaced with H2-antagonists or antacids.

Table 3 Dose Modifications Due to Hematologic Toxicities

Event	AC699 Dose ^a	
Neutropenia (ANC)		
ANC <1.0 -0.5 × 10 ⁹ /L (Grade 3)	Closely monitor patient, diagnose the cause, and treat accordingly	
	If not recovered in 2 weeks: hold drug	
	 if it recovers to ≤ Grade 2, restart at the same dose 	
	- if within 3 weeks of drug hold it does not recover to ≤ Grade 2, resume dose at one lower dose level.	

CONFIDENTIAL

Sponsor/Development Innovations Study Numbers: AC699-001/BRE 401

Final Protocol: 07 May 2024 Version 4.0

This document describes the Statistical Analysis Plan for the Accutar Biotechnology, Inc. AC699-001 (BRE401) study, "A Phase I Clinical Study to Evaluate the Safety, Tolerability, Pharmacokinetics, Pharmacodynamics, and Preliminary Anti-Tumor Activity of AC699 in Patients with Estrogen Receptor Positive/Human Epidermal Growth Factor Receptor 2 Negative (ER+/HER2-) Locally Advanced or Metastatic Breast Cancer."

1.1 **Background and Rationale**

Nearly 80% of breast cancers express estrogen receptors (ER), hormone-regulated transcription factors (DeSantis et al. 2019) and both preclinical and clinical studies highlight an important oncogenic role for estrogen and ERs mediated through proliferation and survival pathways (Spicer and Pike 1993). Several therapies have been developed to antagonize the oncogenic ER function.

A newly emerging technology, E3 ligase-engaged chimeric degraders, has been used to induce more potent and deeper ER degradation. Chimeric degraders degrade a protein of interest by connecting an ER ligand to an E3-recruiting ligand with an optimal linker. This subsequently brings ER within close proximity of E3 ligase and induces subsequent robust ubiquitination and degradation of ER. This is a first-in-human study of the chimeric ER degrader, AC699.

The dose-escalation portion of this study will begin with 100 mg once daily.

1.2 **Objectives**

Table 1 Study Objectives and Corresponding Endpoints

Primary Objective:	Endpoints/Variables:	
Evaluate the safety and tolerability of AC699	Incidence and severity of dose-limiting toxicities (DLTs), treatment-emergent adverse events (TEAEs), and clinically significant Grade 3 or higher laboratory abnormalities	
Secondary Objectives:	Endpoints/Variables:	
Evaluate the preliminary anti-tumor activity of AC699	Objective response rate (ORR [CR+PR]) as defined by Response Evaluation Criteria in Solid Tumors (RECIST) Version 1.1, clinical benefit rate (CBR) (complete response [CR]+partial response [PR]+stable disease [SD] ≥6 months), duration of response (DOR), disease control rate (DCR), and progression-free survival (PFS)	

Characterize the pharmacokinetics (PK) profile of a single dose and after multiple doses of AC699

PK parameters

Exploratory Objectives:

Evaluate the pharmacodynamic effect of AC699 in ERα degradation

Evaluate the relationship between ERα degradation on circulating tumor cells and administration of AC699

Evaluate the relationship between estrogen receptor gene 1 mutation status and antitumor activity of AC699

Evaluate the relationship between circulating tumor DNA levels and antitumor activity of AC699

Endpoints/Variables:

Change of ER α expression in tumors from baseline to post-treatment if tumor tissue is available from paired biopsies

Correlation between circulating tumor cell count at baseline and post-treatment, and anti-tumor activity (ORR, CBR, DOR, DCR, and PFS)

Correlation between estrogen receptor gene 1 mutational status and anti-tumor activity (ORR, CBR, DOR, DCR, and PFS)

Correlation between circulating tumor DNA levels at baseline & post-treatment and anti-tumor activity (ORR, CBR, DOR, DCR, and PFS)

1.3 **Responsibility**

The final statistical analysis of AC699-001 study will be performed by Development Innovations.

2 Study Methods

2.1 Trial Design

This study is a Phase I, first-in-human, open-label dose-escalation study of AC699 given as a single agent. Pending the totality of data, including but not limited to safety and pharmacokinetics, selected dose level(s) may be expanded to approximately 15 patients (per dose level) to further support the evaluation of the objectives set hereabove. Approximately 60 patients may be enrolled in this study.

[figure not shown]
AC699 will be administered orally once daily. The starting dose will be 100 mg once daily on a 28-day per cycle schedule. The dose will be increased a maximum of 2-fold per a 3+3 dose escalation design only following approval from the Safety Review Committee (SRC). If suggested by emerging safety or PK findings, or as appropriate based on other data from previous cohorts, alternative dosing levels and/or dosing schedule may be considered. The

study will identify a maximum tolerated dose (MTD) if possible, assessed with safety and tolerability data. The totality of data collected on AC699 treatment may be used to suggest a recommended Phase II dose.

The planned dose escalation study schema is presented in Figure 1. However, dose levels may be adjusted, and additional dose levels may be tested if suggested by the acquired clinical data and is deemed safe by the SRC.

Figure 1 Study Schema

2.2 Randomization

Not applicable.

2.3 Sample Size Justification

The actual number of dose levels to be explored in this study will depend on determination of the non-tolerable dose based on DLTs. The MTD will be defined based on DLTs. Other safety data, as well as PK profiles observed during the conduct of the study and any trends for anti-tumor activity will also be collected. Treatment cycles will occur consecutively as per the Schedule of Assessments. If one patient experiences a DLT at a given dose level, then that dose level will be expanded to 6 patients. Evaluation of a cohort of at least 3 patients completing 1 cycle of treatment (28 days) is required prior to proceeding to the next dose level. In addition, selected dose levels may be expanded to approximately 15 patients (per dose level).

The study will enroll approximately 60 patients, but the actual number will depend on the actual data.

2.4 **Hypothesis Testing Framework**

Not applicable due to no hypothesis testing being done.

2.5 Statistical Interim Analysis and Stopping Guidance

No formal interim analyses are planned.

2.6 Timing of Final Analysis

The final analysis will take place after the last patient last visit and the database has been locked.

2.7 Timing of Outcome Assessments

Refer to the Schedule of Assessments in the Protocol.

3 Statistical Principles

3.1 *P*-values and Confidence Intervals (CIs)

There are no formal hypotheses for this study. Instead, CIs will be presented.

3.1.1 Confidence Intervals

All CIs will be two-sided 95% exact CIs by Clopper-Pearson unless stated otherwise.

3.2 Protocol Deviations

A protocol deviation is defined as any change, divergence, or departure from the study design or procedures defined in the protocol or as mandated by applicable regulations. Protocol deviations will be classified as major/important or minor. Major/important protocol deviations are those that may significantly impact the completeness, accuracy, and/or reliability of the study data or that may significantly affect a participant's rights, safety, or well-being.

The specific protocol deviation criteria will be listed in the Protocol Deviation Management Plan, which is developed by Development Innovations in consultation with the Sponsor. The protocol deviations will be separate from the database and provided by Development Innovations in an Excel file.

Major/important protocol deviations will be listed.

3.3 Analysis Sets

The following analysis sets (populations) will be used in this study:

- Full/Safety Analysis Set (SAF) is defined as all patients who have received at least one dose of study treatment. Patients will be included in the cohort in which they have been treated.
- Efficacy Evaluable Set (EFF) is defined as all patients who have received any dose of study treatment and have at least one adequate post-baseline response assessment.
- PK Analysis Set is defined as all patients who have received at least one dose of study treatment and have at least one sample collection of blood with a measurable concentration of study drug in plasma.

For safety analyses, participants will be summarized under the actual dose level and the analyses will be performed using the Safety Analysis Set.

For efficacy analyses, participants will be summarized under the initial planned dose level and the primary analysis population will be the Efficacy Evaluable Set.

For all other analyses (e.g., demographics and baseline characteristics), participants will be summarized under the actual dose level and the analyses will be performed using the Safety Analysis Set, unless otherwise specified.

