5.1.2 Intra-patient dose adjustment

Patients may be permitted an intra-patient dose-escalation of AC699 to a higher dose level that does not have any treatment-related AE of Grade 3 or higher and has been cleared and deemed safe by the SRC if they have completed Cycle 1 at their assigned dose level and continued on-study with no \geq Grade 2 treatment-related AEs. The Investigator must consult with the Medical Monitor to confirm if the patient is permitted be dose-escalated to a dose level already cleared by the SRC. The patient data will continue to be collected for evaluation of safety and clinical activity, and all assessments will continue according to the Schedule of Assessments.

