7.3.4 Imaging Assessments

Patients will be evaluated for response after 2 cycles of treatment. Response will be assessed every 2 cycles / 8 weeks (± 5 days) for the first year of treatment, and then every 4 cycles / 16 weeks (± 5 days) thereafter.

The following assessments will be performed if abnormal at baseline or if clinically indicated:

- CT scan of chest/abdomen/pelvis to include adrenal glands (CT scan of abdomen and pelvis required if adrenal glands are not included on CT scan of chest). An MRI may be performed in place of a CT scan at the discretion of the Investigator. However, the same imaging modality should be used throughout the study to image a given lesion.
- CT scan head/MRI brain if history of central nervous system (CNS) metastasis
- Bone scan or CT/PET scan if history of bone metastases.

The assessments to be performed at this time are specified in Appendix B. Please refer to Section 9 for further instructions on evaluating response (e.g., PD, SD).

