6.1.1.1 Dose Calculations

•
$$PDI\left(\frac{mg}{day}\right) = \frac{\sum_{j=1}^{m} Planned\ Dose\ (mg)_{j}}{\sum_{j=1}^{m-1} Planned\ Cycle\ Length\ (days)_{j} + Last\ Cycle\ Length\ (days)_{j}}$$

[Note: Planned Dose is the initial per-protocol dose assigned to the participant.]

•
$$ADI\left(\frac{mg}{day}\right) = \frac{\sum_{j=1}^{m} Actual \ Dose \ (mg)_{j}}{\sum_{j=1}^{m} Actual \ Cycle \ Length \ (days)_{j}}$$

Where j = 1, 2, 3, m are the indices for the cycle, and the cycle length is defined as follows:

Except for last cycle,;

$$Cycle\ Length\ (days) = 28$$

Since participants may discontinue the study treatment at any time, the last cycle may not be a complete cycle of treatment, therefore it needs special attention.

Last Cycle Length (days) = (min [Date of Last AC699 Dose, Date of Death, Date of Data Cut-off] - Date of First AC699 Dose in Last Cycle + 1)

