7.1 Pharmacokinetic Analysis

Plasma concentrations of AC699 will be summarized descriptively at each timepoint.

Plasma concentrations of AC699 will be used to calculate the PK parameters. These parameters will be listed by individual patient and summarized by descriptive statistics (means, medians, ranges, standard deviations, and coefficients of variation as appropriate) by cohort.

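### The SAP has no rule for outcomes after an intra-patient dose change, so by-dose efficacy, TEAE, later PK and RDI summaries can reflect a dose other than the one shown

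*SAP*

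**What the plan says.** Protocol 5.1.2 states: "Patients may be permitted an intra-patient dose-escalation of AC699 to a higher dose level". The patient qualifies "if they have completed Cycle 1 at their assigned dose level and continued on-study with no" related AE of Grade 2 or higher. The target level must be cleared by the SRC and free of related AEs of Grade 3 or higher, and the Medical Monitor must confirm the move. After it, "The patient data will continue to be collected for evaluation of safety and clinical activity". Protocol Section 6 also allows up to two dose reductions. On imaging, Protocol 7.3.4 says: "Patients will be evaluated for response after 2 cycles of treatment".

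The SAP groups data in four ways:
- Efficacy (SAP 3.3): "For efficacy analyses, participants will be summarized under the initial planned dose level".
- Safety (SAP 3.3): "For safety analyses, participants will be summarized under the actual dose level".
- PK parameters (SAP 7.1): "summarized by descriptive statistics (means, medians, ranges, standard deviations, and coefficients of variation as appropriate) by cohort". Concentrations are summarised by timepoint.
- RDI (SAP 6.1.1.1): "Planned Dose is the initial per-protocol dose assigned to the participant".

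The exposure section (SAP 6.1) counts interruptions, modifications and intra-patient escalations, with reasons. SAP Table 4 has no event or censoring row for a dose change, and no sensitivity analysis addresses one.

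**The concern.** The dose-level tables are part of the totality of data that may be used to suggest the RP2D, and SAP 3.5.1 presents the Kaplan-Meier curves as a picture of differences between dose levels. A patient who escalates contributes ORR, CBR, DCR, DoR and PFS to the starting dose even if most of the follow-up was on another dose. The reader of those tables cannot see how much of a dose level's result this concerns. TEAE incidence is a primary endpoint, yet the SAP does not say under which dose a two-dose patient's events belong, so the choice would be made at programming, possibly with the data in view. RDI, meant to show how much of the intended dose was delivered, stops doing so for an escalated patient.

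**Working it through.** The plan is descriptive and gives no figure to reproduce. The checks below use its own schedule; assumed values are marked.

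**1. Timing for efficacy.** Inputs: Cycle 1 lasts 28 days; first scan at Day 56 ± 5; CBR requires SD of at least 24 weeks in the protocol (168 days) and 6 months in the SAP (6 × 30.4375 = 182.6 days).
- Days on the higher dose before the first scan, if the patient escalates at once: 56 − 28 = 28 (range 51 − 28 = 23 to 61 − 28 = 33). No scan is then made on the starting dose alone.
- Share of time on the higher dose at the CBR mark: (168 − 28)/168 = 83%, or (182.6 − 28)/182.6 = 85%.

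This early move mainly concerns backfill patients, for whom a higher cleared level may already exist. If each level needs its own 28-day evaluation, the level above an initial cohort clears no earlier than about 2 × 28 = 56 days after that cohort starts.

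**2. Weight of one response.** 1/20 = 5 points; 1/6 = 17 points; 1/3 = 33 points.

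**3. Effect on an ORR (assumed counts).** With 20 patients and 4 responders, ORR is 20.0% (Clopper-Pearson 95% CI 5.7 to 43.7). If 1, 2 or 4 of them first responded after escalation and are counted as non-responders, ORR is 15.0% (3.2 to 37.9), 10.0% (1.2 to 31.7) or 0% (0 to 16.8). The denominator matters: if 5 patients escalate before any scan, 2 of them responders, and are shown separately, the result is 2/15 = 13.3% (1.7 to 40.5), not 2/20 = 10.0%.

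**4. Effect on a dose contrast (assumed rates).** Let f be the fraction of low-dose patients who escalate, and assume they respond at the high-dose rate. The apparent low-dose rate is (1 − f) × p_low + f × p_high, and the apparent difference is (1 − f) × (p_high − p_low).

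| f | 10% vs 30%: apparent low / difference | 10% vs 20%: apparent low / difference |
|---|---|---|
| 0 | 10 / 20 | 10 / 10 |
| 10% | 12 / 18 | 11 / 9 |
| 25% | 15 / 15 | 12.5 / 7.5 |
| 50% | 20 / 10 | 15 / 5 |

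If the two doses are equally active, the shift is zero at every f.

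**5. Safety.** DLTs are assessed in the first 28 days, before escalation is possible, so they are untouched. For TEAEs, placing the patient under the first dose puts later events at too low a dose. Placing the patient under the later dose puts Cycle 1 events at too high a dose, and adds to that level people selected for having had no related AE of Grade 2 or higher. The SAP does not choose.

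**6. PK.** Scheduled samples through Cycle 6 Day 1: 7 + 7 + 4 = 18. The two Cycle 1 profiles and the Cycle 2 Day 1 pre-dose sample, 7 + 7 + 1 = 15, precede any escalated dose. That leaves 3 of 18 (pre-dose at Cycles 3, 4 and 6), plus optional samples after a dose change (up to 14 in repeat profiles and 3 troughs), without a clear dose rule.

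**7. RDI (illustrative doses).** RDI = ADI/PDI. One cycle at 100 mg and five at 400 mg give ADI = (1 × 100 + 5 × 400)/6 = 350 mg/day. PDI is 100, so RDI = 350%. With 200 mg instead, (1 × 100 + 5 × 200)/6 = 183 mg/day, or 183%. In a level of 20 with 19 patients at 80% and one at 350%, the mean is (19 × 80 + 350)/20 = 93.5%; the median stays at 80%.

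**The case against.** The strongest reply is that grouping by the initial planned dose is a recognised, prespecified convention. It compares starting-dose strategies and avoids selecting on what happens later. There is no hypothesis test, and all efficacy and safety data are listed. This stands: the initial-dose summary should stay, and it is not an error of assignment.

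Several stronger readings are tempting, and the documents do not support them:
- A reader might infer that low doses will look too active. That requires higher doses to be more active, which is not established, and enough escalations to matter, which the documents do not quantify. The conditions on the target level and the Medical Monitor's confirmation limit the number.
- A reader might infer that the PK parameters mix doses because they are summarised by cohort. The scheduled profiles are complete before any escalation; the later troughs are concentrations, a separate sentence in SAP 7.1. They fall back on the actual dose level in SAP 3.3, which has the same two-dose ambiguity.
- A reader might infer that RDI hides interruptions. SAP 6.1 tabulates these separately, and SAP 3.4.5 requires the median, minimum and maximum. Nor can an extreme mean arise in an initial 100 mg cohort from five of six cycles at 400 mg: with steps of at most 2-fold, that level clears no earlier than about 3 × 28 = 84 days in.
- A reader might infer that the MTD is compromised. It rests on DLTs, which are unaffected.

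A fair criticism of the remedy also stands. Cutting data at escalation leaves some patients with no scan at all, and the censoring may be informative because escalation is selected on tolerability. Upward moves are also not the only source of mixing; reductions do the same.

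**Conclusion.** The point holds as a gap in supportive analysis and in definitions. By-dose ORR, CBR, DCR, DoR and PFS can reflect a dose other than the one they are shown under, and nothing in the SAP lets a reader see how far. The actual dose level for TEAEs is undefined for a two-dose patient. RDI can exceed 100% and its mean can be inflated, although medians and interruption summaries remain. The PK gap is confined to the Cycle 3, 4 and 6 troughs and optional repeat profiles.

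The size is unknown because the number who will escalate is not given; it is zero if nobody does. Its direction depends on whether higher doses are more active. The response counts, response rates, escalation fractions and RDI values above are assumptions for illustration. The timing and sample counts come from the documents. The change is cheap and should be made before database lock, so that attribution is not settled after the data are seen.

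**What to change.** Keep the initial-dose efficacy summary and add the following to the SAP:
- **Efficacy (3.3, 5.2).** A flagged listing of patients with an intra-patient escalation or reduction, giving the dose at first response and at progression. Also a sensitivity analysis of ORR, CBR, DCR, DoR and PFS at the starting dose using only data up to escalation. State the denominator; for example, show patients who escalate before any scan separately and do not count them as non-responders. Note that censoring at escalation may be informative.
- **Safety (3.3, 6.2).** TEAE tables by the dose level being taken at onset.
- **PK (7.1).** Post-Cycle 1 concentrations and any repeat profiles summarised by the dose being taken at sampling.
- **RDI (6.1.1.1).** PDI calculated from the assigned dose including permitted escalations, with unplanned reductions and interruptions still counted against it.

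The cost is SAP wording and a few extra tables. Shorter follow-up and possible informative censoring affect the sensitivity analysis only.
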